3.0 Scientific Endpoints*

2.1 Describe the scientific endpoint(s), the main result or occurrence under study.

*NOTE: Scientific endpoints are outcomes defined before the study begins to determine whether the objectives of the study have been met and to draw conclusions from the data. Include primary and secondary endpoints. Some example endpoints are: reduction of symptoms, improvement in quality of life, or survival. Your response should **not** be a date.*

Response: The two primary outcome measures will be the motion and the muscle activation data of the lower body during walking. Motion trajectory will be used to detect the changes in the kinematics and sEMG data will present the muscle activation of the participants. Ground reaction force, center of pressure, and center of mass will be evaluated with the instrumented insole and treadmill. Before the first and after the last training, participants will be evaluated for functional gait assessment, 6-min-walk, leg strength using dynamometer, international physical activity questionnaire (short form), usability questionnaire, and Modified Ashworth test by a physical therapist. This will show the kinematic and kinetic changes of the participant after the training.

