of training with a cable-actuated robot will be provided. The device will augment 15% of their own body weight. While they are walking with the device, auditory feedback will be provided for the participants who are assigned to the auditory group. The auditory and non-auditory groups will be randomly assigned. Furthermore, one of the 3 different types of auditory feedback will be randomly assigned to participants from the feedback group. A break of 5 minutes will be provided after 10 minutes of walking with the device. After the robotic training is completed, the device will be taken off and the participant will walk without the device to monitor the immediate retention of the training. After every 10 minutes, the researcher will ask the participant questions as per the Borg exertion scale to check the fatigue of the participant. After finishing the treadmill session, participants will take a 10-minute break and walk 4 minutes with (or without auditory feedback) on the floor. The participant will repeat overground walking for a total of three sets. There will be a total of ten training sessions, two or three sessions a week and each session will last for a maximum of 3 hours. In addition, pre and post-training visits are required to evaluate functional gait assessment, 6-min-walk, leg strength using a dynamometer, international physical activity questionnaire (short form), usability questionnaire, and Modified Ashworth test by a physical therapist.

12.2 Describe what data will be collected.

NOTE: For studies with multiple data collection points or long-term follow up, consider the addition of a schedule or table in your response.

Response:

- We will schedule the participants to visit the lab. We will make a table when the participants are available.
- *EMG data from the muscles*
- *Vicon motion capture data*
- *Photo and Video of the test*
- *IMU sensor data*
- *Smart insole data*
- *Ground reaction force*

12.3 List any instruments or measurement tools used to collect data (e.g. questionnaire, interview guide, validated instrument, data collection form).

Include copies of these documents with your submission.

Response: Vicon motion capture system, Delsys Trigno sEMG system, and Bertec Force plate instrumented treadmill, Smart Insole

12.4 Describe any source records that will be used to collect data about subjects (e.g. school records, electronic medical records).

Response: N/A

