19.0 Data Management and Analysis*

19.1 *Describe the data analysis plan, including any statistical procedures. This section applies to both quantitative and qualitative analysis.*

Response: The collected motion capture data will be labeled and filtered with a 4th order Butterworth filter. All sEMG data will be post-processed by bandwidth filter, enveloped, smoothed, and scaled. To define the beginning and the end of each repetition the speed of the markers is used as a threshold. The data will be time-scaled and averaged over different trials.

The analyses for CP subjects are carried out separately. Descriptive statistics will be obtained to compare the randomized groups on baseline factors including pre-existing chronic conditions, underlying disease, demographics, and other potential confounders. When the numeric data are not normally distributed based on graphic inspection (e.g., normal quantile plots), we will consider the Box-Cox transformation. For numeric data, a mixed-effects model will be constructed, where

major factors include the effect of time within each day, the effect of feedback, the effect of the day as well as the effect of the random assignment. Major statistics to obtain will be improvement measures between baseline and the end of treatment. An appropriate covariance structure will be considered reflecting the correlations within subjects. Various contrasts will be tested to see an improvement by the major factors. Some other covariates such as demographic and other subjects characteristics can be included in the models if a significant difference is shown. Residual plots will be examined to check the normality of the residual. If not normally distributed, we will consider simpler nonparametric methods that compare specific factor combinations in a form of various contrasts. For categorical data, we will construct a similar model to the numeric data, except that we will use an appropriate link function based on the generalized linear model. The covariance structures will be incorporated into the analysis using a generalized structural equation modeling strategy. For this pilot study, we do not consider controlling family-wise Type I error as the purpose of the study is to see the viability of the treatment and potentially support the bigger clinical trials in the future.

19.2 If applicable, provide a power analysis.

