NOTE: This may not apply to certain types of studies, including chart/records reviews, survey studies, or observational studies. This question is asked to elicit whether the investigator has an adequate sample size to achieve the study objectives and justify a conclusion.

Response: A goal of this study is to test the feasibility and efficacy of the proposed intervention in the improvement of gait characteristics. Currently, no previous study is available to have the treatments both resistance training and sensory feedback. For CP subjects, we will have a sample size of 20 (10 each group), which requires an effect size of 0.5 to have a power of 80% with the size of the test 0.05 in the two-group comparison with 6 repeated measures under the assumption of compound symmetry with auto-correlation 0.1.

19.3 Describe any procedures that will be used for quality control of collected data.

Response: The post-processed data will be visually investigated whether all the procedures were properly applied. Outliers will be also detected during this investigation.

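### Section 19.2 states 80% power without defining what is powered; the same inputs give 56% to 61% for a six-measure mean and about 12% to 41% for the baseline-to-end improvement that 19.1 analyses

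*Combined protocol and SAP*

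**What the plan says.** Section 19.2 gives one power statement. Its inputs are 20 participants split equally, an effect of 0.5, 80% power and alpha 0.05, and it describes the setting as a "two-group comparison with 6 repeated measures under the assumption of compound symmetry with auto-correlation 0.1". It does not say which outcome or contrast is powered, which occasions make up the six measures, in what units 0.5 is expressed, or whether the test is one- or two-sided.

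Section 19.1 plans a mixed-effects model with effects for time within the day, day, feedback and random assignment, tested through contrasts. It then states the focus: "Major statistics to obtain will be improvement measures between baseline and the end of treatment".

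On the schedule, Section 12.1 says "There will be a total of ten training sessions, two or three sessions a week", with further visits before and after training; Section 5.1 treats ten as a maximum. The clinical tests come once at each end (Section 3.0): "Before the first and after the last training, participants will be evaluated for functional gait assessment, 6-min-walk, leg strength using dynamometer". No section describes a set of six occasions.

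**The concern.** A power figure belongs to one particular contrast. Under compound symmetry with a low correlation, the choice of contrast matters a great deal. A correlation of 0.1 makes an average over several measures precise, because the measures carry nearly independent information. The same correlation makes a change score imprecise, because the baseline explains almost none of the end value. An input that favours one contrast therefore works against the other.

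Section 19.2 names no contrast, while 19.1 names baseline-to-end improvement. If the 80% does not apply to that improvement, readers of the result, and anyone using this pilot to plan a larger trial, will take the group comparison to be much more sensitive than it is.

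**Working it through.** **Inputs from 19.2:** n = 10 per group, effect 0.5, alpha 0.05, m = 6 measures, compound symmetry with rho = 0.1. **Assumptions where 19.2 is silent:** 0.5 is a total between-group difference in SDs of one measurement (sigma = 1), and the test is two-sided. One-sided figures are added where they matter.

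**Method.** For a contrast with standard deviation s, the noncentrality is 0.5 / (s × √(2/10)). Power is from the noncentral t (18 df, or 17 when adjusted for baseline), with the normal approximation alongside where given.

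**1. Trying to reproduce the 80%: mean of six measures**
- Variance = (1 + 5 × 0.1)/6 = 0.25, so s = 0.5.
- Noncentrality = 0.5/(0.5 × 0.4472) = 2.236.
- Two-sided power is 56% (t) or 61% (normal). One-sided it is 69% or 72%.
- On this reading, 80% two-sided power needs an effect of 0.66 (t) or 0.63 (normal), or 16 per group at 0.5 (normal).

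The printed figure is not reproduced.

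**2. What does come near 80%**
- Within-subject (slope) formula: variance (1 − 0.1)/6 = 0.15, s = 0.387, power 78% (t) or 82% (normal). The matching sample size is 2 × (1.96 + 0.842)² × 0.9/(6 × 0.5²) = 9.4, so 10 per group. Here 0.5 has to be a slope difference per SD of time. Over six equally spaced points the SD of time is √(17.5/6) = 1.708 and the span is 5, so the total difference is 0.5 × 5/1.708 = 1.46 SD, not 0.5 SD.
- Independent measures (rho = 0): 78% (two-sided, normal). This changes the stated correlation.
- AR(1) instead of compound symmetry: 81% (one-sided, normal). This changes the stated structure.

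**3. Baseline-to-end improvement compared between groups (t, two-sided)**

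| Contrast | Variance | s | Power at 0.5 |
|---|---|---|---|
| Change, one value at each end | 2(1 − 0.1) = 1.8 | 1.342 | 12% |
| End value adjusted for baseline | 1 − 0.1² = 0.99 | 0.995 | 19% |
| Mean of three late minus mean of three early | 2(1 − 0.1)/3 = 0.6 | 0.775 | 28% |
| Mean of three late adjusted for mean of three early | 0.4 − 0.1²/0.4 = 0.375 | 0.612 | 41% |

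In the last row, the variance of a three-measure mean is (1 + 2 × 0.1)/3 = 0.4 and the covariance of the two means is 0.1. The three-and-three layout is assumed. If 0.5 is instead in SDs of the change itself, power with one value at each end is 19%.

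**4. Detectable effect.** With 10 per group, 80% two-sided power needs about 1.78 SD for the single change and about 1.32 SD for the baseline-adjusted end value.

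**5. Other correlations (assumed range; the plan states 0.1).** Power for the single change is 18% at 0.5, 39% at 0.8 and 66% at 0.9. It reaches 80% only at about 0.93.

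**The case against.** The strongest reply is that the contrast in 19.1 is less fixed than a single change score. The model includes time within the day, data are averaged over trials, and each session contains several walking periods, so each end of the comparison could rest on several recordings. Objective 1 concerns the benefit of training itself, so improvement is not only a group difference. The plan also calls itself a pilot and waives family-wise error control.

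Much of this stands. It is why 12% to 19% cannot be presented as the only answer and why the three-and-three figures are given. It does not rescue the 80%: the more generous layout reaches 41%. Section 19.2 itself describes a two-group comparison, so the group contrast is the one to check. Pilot status could justify giving no power figure, but it does not make a printed one right.

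Three stronger readings are tempting and are not supported:
- A reader might infer that the trial was sized on an average of six measures. Section 19.2 never mentions averaging, and the average does not give 80%. The slope formula comes closer, so the basis used is unknown.
- A reader might infer that 19.2 claims 80% for the functional gait assessment, 6-minute walk, strength and Ashworth tests, which have only two assessments. It refers to gait characteristics, and Section 3.0 names motion and muscle activation as primary.
- A reader might infer that a null result will be reported as evidence against feedback. No section says so; this is a risk created by the printed figure.

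**Conclusion.** The concern holds in this form: the 80% in 19.2 is attached to an undefined contrast, and the stated inputs do not deliver it for the analysis in 19.1. With 0.5 as a total difference in single-measure SDs and a two-sided test, none of the group contrasts tried under the stated correlation reaches 80%. The highest is the six-measure mean, at 56% to 61%. The improvement comparison lies between about 12% and 41%, depending on how many values stand at each end and whether baseline is adjusted for.

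The exact figure rests on an effect scale, a sidedness and a layout that the plan does not give. That the power is well below 80% holds across the layouts examined at the stated correlation. Getting to about 80% requires a different correlation or covariance structure, or reading 0.5 as a slope per SD of time, which is a total difference of about 1.46 SD.

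**What to change.** In 19.2, first define what is being powered: the outcome, the group contrast (matching 19.1), the occasions counted as repeated measures, the units of the effect size, and whether the test is one- or two-sided. Then replace the 80% with the power, or the detectable effect, for that contrast. For example, for a single baseline-to-end change at correlation 0.1 with 10 per group and two-sided 0.05, power at 0.5 SD is about 12%, and 80% power needs about 1.78 SD. No figure should be printed until those inputs are settled.

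If the sponsor wants to keep the gain from repeated measures, 19.1 could name the baseline-adjusted mean of the post-baseline recordings as the major group contrast, with its power printed in 19.2. Assuming one baseline and five later measures, the variance is (1 + 4 × 0.1)/5 − 0.1² = 0.27 and power at 0.5 is about 53%.

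The cost is wording in 19.1 and 19.2, with no added participants or visits. The printed figure becomes less favourable, which a pilot can accept. An averaged contrast would describe the course of training rather than its end.

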8.0 Inclusion and Exclusion Criteria*

8.1 *Describe the criteria that define who will be **included** in your final study sample.*

NOTE: This may be done in bullet point fashion.

Response: The inclusion criterion for the study is adults with cerebral palsy (18-65 years old) who can ambulate a distance of 100 feet with or without the use of assistive devices. However, they shouldn't need physical assistance from a caregiver while they walk 100 feet.

8.2 *Describe the criteria that define who will be **excluded** from your final study sample.*

NOTE: This may be done in bullet point fashion.

Response: Recruited participants will be excluded if they have severe Equinovarus foot or Genu recurvatum of the knee. Participants who had surgery within 6 months will be excluded. Individuals with pregnancy, lower limb prosthetics, severe respiratory problems such as chronic obstructive pulmonary disease, heart disease, a loss of sensation, uncontrolled blood pressure, a seizure disorder, severe arthritis will be excluded from this study.

8.3 *Indicate specifically whether you will include any of the following special populations in your study using the checkboxes below.*

NOTE: Members of special populations may not be targeted for enrollment in your study unless you indicate this in your inclusion criteria.

Response:

- Adults unable to consent
- Individuals who are not yet adults (infants, children, teenagers)
- Pregnant women
- Prisoners

8.4 *Indicate whether you will include non-English speaking individuals in your study. Provide justification if you will exclude non-English speaking individuals.*

*In order to meet one of the primary ethical principles of equitable selection of subjects, non-English speaking individuals may **not** be routinely excluded from research as a matter of convenience.*

In cases where the research is of therapeutic intent or is designed to investigate areas that would necessarily require certain populations who may not speak English, the researcher is required to make efforts to recruit and include non-English speaking individuals. However, there are studies in which it would be reasonable to limit subjects to those who speak English. Some examples include pilot studies, small unfunded studies with validated instruments not available in other languages, studies with numerous

questionnaires, and some non-therapeutic studies which offer no direct benefit.

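### Section 19.2's 80% power at an effect size of 0.5 does not follow from its own inputs (about 56% two-sided), and the detectable effect depends heavily on an unsourced correlation of 0.1 and an unnamed contrast

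*Combined protocol and SAP*

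**What the plan says.** Section 19.2 of the combined protocol and SAP plans for 20 participants, split equally between two arms, and claims that at a 5% test level this gives 80% power for an effect of 0.5. The calculation is described as using "6 repeated measures under the assumption of compound symmetry with auto-correlation 0.1". It does not say whether the test is one- or two-sided, which outcome is meant, which SD scales the effect size, which six occasions are counted, or where 0.1 comes from. No other within-person correlation appears in the document.

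Section 19.1 describes the analysis that this power figure should support: a mixed-effects model whose covariance structure is to be chosen later. On the summary of interest it says "Major statistics to obtain will be improvement measures between baseline and the end of treatment". It also says of the processed signals: "The data will be time-scaled and averaged over different trials".

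**The concern.** The power paragraph is the plan's only quantitative support for 20 participants. Section 19.2 names efficacy as well as feasibility as a goal, and Section 19.1 hopes the pilot may support larger trials. A reader will conclude that a between-group difference of half an SD is likely to be detected.

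There are two reasons to doubt this. First, the claimed power looks high for 10 per group even with six measures each. Second, the result leans on one correlation. Under compound symmetry, 0.1 means that only 10% of the variance is stable difference between people, so six measures act almost like independent data. That favours a group comparison of averages. It works against a change from baseline, where a low correlation adds noise. So one correlation with no stated contrast does not fix the detectable effect, even roughly.

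**Working it through.** **Inputs from Section 19.2:** 10 per group; alpha 0.05; effect size 0.5; six measures; compound symmetry with correlation r = 0.1.

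**Assumptions added here:** 0.5 is a mean difference divided by the SD of one measurement; all 20 participants complete; other values of r, up to 0.9, are assumed.

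**Method.** With per-person variance v (in units of the single-measure variance), the standard error of the group difference is sqrt(2v/10). For 80% power, the noncentral t with 18 df gives a detectable effect of 2.963 × sqrt(2v/10) two-sided, or 2.586 × sqrt(2v/10) one-sided. The normal approximation replaces 2.963 by 1.960 + 0.842 = 2.802.

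**Step 1: the plan's own figure.** For the mean of six, v = (1 + 5r)/6 = (1 + 0.5)/6 = 0.25, so sqrt(2 × 0.25/10) = 0.2236.

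- Two-sided: 2.963 × 0.2236 = 0.66 SD; power at 0.5 is 56%. Normal approximation: 0.63 SD and 61%.
- One-sided: 2.586 × 0.2236 = 0.58 SD; power at 0.5 is 69%. Normal approximation: 0.56 SD and 72%.
- Even by the normal approximation, 80% power at 0.5 would need 16 per group two-sided or 13 one-sided.

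**Step 2: other readings of 19.2.**

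- Repeated-measures F tests with f = 0.25 (equivalent to a difference of 0.5 SD) give 56% for the group effect and 55% for the interaction.
- Reading 0.5 itself as f gives about 99%.
- A value near 0.5 appears only if a stated input is changed. Setting r = 0 gives 0.51 (two-sided, normal). A correlation that decays with lag from 0.1 has v = 0.197 and gives 0.49 (one-sided, normal). The second is not compound symmetry.

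No reading tried that keeps the stated inputs returns 80%.

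**Step 3: dependence on r and on the contrast.** Two-sided 0.05, 10 per group:

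- A, unadjusted mean of six: v = (1 + 5r)/6.
- B, end minus baseline: v = 2(1 − r).
- C, mean of five later measures with one baseline as covariate: v = (1 + 4r)/5 − r². One degree of freedom is charged for the covariate (17 df, multiplier 2.973).

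| r | A: v, detectable SD, power at 0.5 | B: v, detectable SD, power at 0.5 | C: v, detectable SD, power at 0.5 |
|---|---|---|---|
| 0.1 | 0.25, 0.66, 56% | 1.80, 1.78, 12% | 0.27, 0.69, 53% |
| 0.5 | 0.583, 1.01, 28% | 1.00, 1.32, 19% | 0.35, 0.79, 43% |
| 0.7 | 0.75, 1.15, 23% | 0.60, 1.03, 28% | 0.27, 0.69, 53% |
| 0.9 | 0.917, 1.27, 20% | 0.20, 0.59, 66% | 0.11, 0.44, 89% |

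Example, B at r = 0.1: 2.963 × sqrt(2 × 1.80/10) = 2.963 × 0.600 = 1.78.

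**Step 4: where 80% at 0.5 would hold.** For C at r = 0.87, v = (1 + 3.48)/5 − 0.757 = 0.139 and the detectable effect is 2.973 × sqrt(0.0278) = 0.50, so r must be about 0.87 or more. For B, 0.4(1 − r) must equal (0.5/2.963)² = 0.0285, so r must be about 0.93 or more. For A, no r from 0.1 to 0.9 suffices.

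**The case against.** The best defence is that nothing in the document shows 0.1 to be wrong. The six measures are undefined. If they are within-session changes, each session's starting value has been subtracted, stable differences between people are largely removed, and a low correlation is plausible. Section 19.1 also scales the sEMG signals, and sensors are attached for the lab visits, which could add visit-to-visit variation. All of this stands.

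A reader might nevertheless infer that Section 19.2 contradicts Section 19.1 and that the true correlation is 0.5 to 0.9, because values are averaged over trials and because eligibility is broad, taking adults of 18 to 65 "who can ambulate a distance of 100 feet with or without the use of assistive devices". The documents do not support that. Section 19.1 states no correlation, 0.1 may already describe averaged values, and a wide eligibility range does not establish a correlation.

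A reader might also infer that choosing improvement as the statistic commits the plan to a correlation above 0.5, since 2(1 − r) falls below 1 only there; at 0.1 it is 1.8. But measuring improvement follows from the hypothesis in Section 2.2 that training improves walking and posture. It is not a claim about precision.

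Finally, this is a pilot with a fixed sample, and the covariance structure will be settled at analysis. That limits the consequence. It does not make the stated power correct.

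**Conclusion.** The concern holds in this form: the stated 80% is not delivered by the stated inputs, and neither the correlation nor the contrast is specified well enough to repair it. The shortfall at the plan's own 0.1 is 24 percentage points two-sided (56% against 80%) and 11 one-sided (69%). Of the three contrasts tabulated, only the baseline-adjusted mean reaches the claim within the range 0.1 to 0.9, and only near the top of it.

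It would be too strong to say that the trial really detects 1.0 to 1.3 SD because the correlation is too low. That range applies only to a mean of six that ignores baseline, at assumed correlations of 0.5 to 0.9. It would also blame the correlation for a gap that already exists at 0.1. For end minus baseline a higher correlation helps.

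The figures rest on single-measure SD units, a constant correlation, complete data, and an assumed correlation range. If participants are lost, power is lower.

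**What to change.** Keep 20 participants. In Section 19.2:

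- Name the contrast and the occasions that enter it, matched to improvement from baseline in Section 19.1. Preferably use the baseline value as a covariate, and say so in Section 19.1 as well.
- State whether the test is one- or two-sided and which SD scales the effect.
- Name one correlation structure, compound symmetry, and drop the term auto-correlation, which suggests decay with lag.
- Replace 80% power at 0.5 with the detectable effect for that contrast over correlations of 0.1 to 0.9, labelled as assumed. For a two-sided baseline-adjusted mean of five later measures this would read about 0.69 SD at 0.1, 0.79 at 0.5 and 0.44 at 0.9.

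The team's 15-session data described in Section 6.0 come from six children with crouch gait and diplegia. They can be cited only as rough support, because the sample is too small and the population differs.

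The cost is one rewritten paragraph, a sentence in Section 19.1 and, if baseline is a covariate, one degree of freedom (less than 0.01 SD in the detectable effect). The stated figure becomes less favourable over most of the range. No extra participants are needed.
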